8.4 Withdrawal of individual subjects

Subjects can leave the study at any time for any reason if they wish to do so without any consequences. Subjects can withdraw from the study by writing the coordinating investigator a letter, stating that they would like to withdraw from the study. The investigator can decide to withdraw a subject from the study for urgent medical reasons.

8.4.1 Specific criteria for withdrawal (if applicable)

Not applicable.

8.5 Replacement of individual subjects after withdrawal

In case a patient decides to withdraw from the study, a new patient will be recruited if

possible. If a patient decides to withdraw from the study prematurely because of clinical complaints during the prolonged moderate-intensity exercise, no new participant will be recruited. The data that have been obtained before termination will then be used as much as possible during data analysis.

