3. STUDY DESIGN

This is a randomised, blinded, placebo controlled, two-way cross over trial. Patients with VLCADD will be recruited by the VLCADD Expertise Center at UMC Utrecht. Nutritional ketosis will be compared to a placebo, delivered as an isocaloric drink before exercise. An individualised, standardised bicycle exercise protocol will be completed by each participant with collection of blood metabolites, respired gases, and subjective ratings of fatigue and muscle complaints. In addition in vivo ³¹P MR Spectroscopic recordings will be made from the quadriceps muscle before (resting), during and post-exercise. An optional muscle biopsy will be obtained from the quadriceps before and after exercise.

Patients will be asked to participate in three study sessions:

session I (site: nearest Academic Medical Center, Pediatric test ward).

- standard maximal cardiopulmonary exercise test (CPET; bicycle ergometry with indirect calorimetry)
objective: determination of VO_{2max} in order to set the desired exercise workload of maximal individual rate of fat oxidation (FATMAX; typically ~40% MVO_2) in sessions II and III below.
- venipuncture
objective: measure rise in blood lactate and creatine kinase (CK) levels in response to CPET

sessions II and III (site: Neuroimaging Magnetic Resonance Center UMC Groningen).

- venipuncture + canulation
objective: prepare subject for serial (every 10 min) blood sampling for off-site metabolic profiling
- oral intake of nutritional drink A or B (ketone and placebo drinks, respectively)
Each subject will receive both drinks over the course of the trial in a blinded fashion – i.e., if drink A in session II, then drink B in session III, and vice versa.
- microbiopsy from the quadriceps muscle (optional)
*1st biopsy: 20 min after oral drink; 2nd biopsy: immediately following end of exercise bout.
objective: metabolomic profiling of the state of the energy metabolic network in muscle and mapping of individual phenotypic muscle properties (fiber type, mitochondrial density, capillary density). Biopsies will be obtained from the m. vastus lateralis of the left leg. Hereto, a preparatory superficial incision of the skin and fascii will be made under local sedation and bandaged, allowing fast and reproducible biopsy sampling prior to and immediately following exercise bout 1 below.*

- 40 min upright bicycling exercise at FATMAX outside MR scanner (exercise bout 1)

Blood samples are collected every 10 minutes.

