Subjects state subjective fatigue and muscle ache following exercise bout.

- microbiopsy from the quadriceps muscle (optional)

Biopsies will be obtained from the m. vastus lateralis of the left leg (see above).

- 5 min supine bicycling exercise at FATMAX inside MR scanner (exercise bout 2)

*serial in vivo 31P MR spectra will be recorded non-invasively from the m. vastus lateralis of the right leg as previously (protocols **12-211/K** (VLCAD; UMC Utrecht); **NL41313.042.12** (MCAD; UMG) to determine energy and proton balance in the muscle during exercise and the kinetics of metabolic recovery following exercise. Subjective fatigue and muscle ache scores and a blood sample will be taken after the subject has exited the scanner room. Final blood samples including on-site analysis of CK levels are taken up to 3 hr post-session III to monitor any rhabdomyolytic event.*

- 24 hours after session II and III, co-investigator [name] will call each subject to evaluate subjective fatigue and muscle complaints after the subject left the test facility.

Time interval between study sessions I and II will be at least 7 days; between study sessions II and III: 7 days. The night prior to sessions II and III, patients will be housed in close vicinity to the UMCG. Patients will be instructed to take a late evening snack or meal according to their individual record of maximal fasting duration, given a start time of the study at 08:00 am the following day. Patients will be allowed a light breakfast according their normal diet before they will receive the caloric drive before the test. The breakfast will be the same for session II and III.

The total duration of the first session will be around 45 minutes, with 30 minutes of preparation and 8-12 minutes of cycling (exact time length dependent on the maximal endurance of the participant). The total duration of the second and third session will be around 5 hours including 45 minutes of preparation, 45-60 minutes of bicycling for the submaximal endurance exercise test and 3 hours of post-exercise resting where after the last blood and urine sample will be collected. During this 3 hour period, participants will be asked to fill out a HAES diary and can watch a DVD to pass time.

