8.2 Randomisation, blinding and treatment allocation

Patients will be handed an unlabeled caloric drink (placebo and ketone ester drink) prior to the endurance exercise bout in each of the two study sessions at UMCG. All patients will receive both drinks over the course of the study. [name], who will

conduct the studies at UMCG together with PI [name], will plan, randomize and record the order of placebo and ketone ester administration to the patients. [name], who will analyze all MRS data, will not have, nor seek access to, these records thus ensuring blinded MRS data analysis.

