10 STATISTICAL ANALYSIS

10.1. Descriptive statistics

Data will be expressed both quantitatively (values of PCr, ATP, Pi, pH, rate constants tau_PC_r and tau_Pi, expressed as median and range), and qualitatively (MRS-spectra).

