10.2 Univariate analysis

Results will be presented by means of confidence intervals. The significance level will be set at $p < 0.05$. Statistical analysis of the results will be performed using standard two-sided Mann-Whitney testing and will be conducted using Origin software (Caltech, USA, version 6.1).

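### Section 8.5, combined with the unpaired test in 10.2, lets a patient with one session count for one drink only, which can bias the ketone-placebo contrast in either direction

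*Protocol*

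**What the plan says.** The design section states: "This is a randomised, blinded, placebo controlled, two-way cross over trial". Section 8.2 adds: "All patients will receive both drinks over the course of the study". Section 4.1 sets the sample at six patients.

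Section 8.5 deals with withdrawal. For a patient who leaves because of clinical "complaints during the prolonged moderate-intensity exercise, no new participant will be recruited". It continues: "The data that have been obtained before termination will then be used as much as possible during data analysis". It does not say how a patient with one usable session enters the comparison of drinks.

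Section 10.1 gives the spectroscopy values "expressed as median and range"; I read this as by drink. Section 10.2 states: "Statistical analysis of the results will be performed using standard two-sided Mann-Whitney testing", at the 0.05 level.

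The main endpoints (8.1.1) are muscle Pi, PCr and pH during exercise versus rest, and the recovery rate constants. The exercise and recovery data come from the "5 min supine bicycling exercise at FATMAX inside MR scanner (exercise bout 2"), which follows the 40-minute upright bout. Completion of each bout, and the minutes cycled if not completed, are secondary endpoints (8.1.2).

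**The concern.** A cross-over removes differences between patients only if both drinks are compared over the same patients. Section 8.5 keeps a lone session, and the Mann-Whitney test accepts six values against five without complaint. Nothing in sections 8.5 or 10 keeps that lone value out of the contrast or the by-drink medians and ranges.

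The loss is unlikely to be random. A patient who leaves because of complaints during exercise is plausibly among the more affected, and with six patients that person is a sixth of the sample. The sign of the resulting bias depends on when the patient leaves, so it could not be corrected afterwards by argument. The event is realistic: the protocol's own rationale for including adolescents says most older patients are unable to complete the study procedures.

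**Working it through.** The protocol states no figure to reproduce: section 4.4 gives no SD, power or formula, and no stopping rate appears anywhere.

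**Inputs.** From the protocol: n = 6, two drinks per patient, unpaired test, exercise spectroscopy only in bout 2. Assumed: no true drink effect, total SD 1, within-patient correlation ρ of 0.5 to 0.9, low value = poor.

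**Who contributes what on the exercise and recovery endpoints**

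| Course | Data available | Effect on unpaired contrast |
|---|---|---|
| Stops in bout 1 of session II, not scanned, leaves | none | none |
| Completes session II, stops in bout 1 of session III, not scanned | session II drink (tolerated) | against the better tolerated drink |
| Complaints in session II, still scanned, does not return | session II drink (poorly tolerated) | against the worse tolerated drink |

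**Size if the most affected patient is lost from one side.** The expected lowest of six standard normal values is −1.267. If the patient is picked out by underlying severity, whose SD is √ρ, the five-value side rises by 1.267 × √ρ / 5 while the six-value side stays centred on zero:

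- ρ = 0.5: 1.267 × 0.707 / 5 = 0.18 SD
- ρ = 0.7: 1.267 × 0.837 / 5 = 0.21 SD
- ρ = 0.9: 1.267 × 0.949 / 5 = 0.24 SD

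Simulated differences in medians are 0.17 to 0.20 SD over the same range. The mean over the five complete pairs has bias 0.00 in this setting. The same sizes apply with the sign reversed in the third row of the table.

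**Size if the patient lies a fixed distance from the others.** One patient 1 to 2 SD worse moves a six-patient mean by 1/6 = 0.17 to 2/6 = 0.33 SD.

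**If stopping depends on the value in that very session.** Let the lost value be the lowest of the six placebo values. The unpaired bias is 1.267 / 5 = 0.25 SD. On complete pairs it is (1 − ρ) × 1.267 / 5: 0.13 SD at ρ = 0.5, 0.08 at 0.7 and 0.03 at 0.9. Pairing reduces this bias but does not remove it.

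**Averaged over random order and stopping.** A null simulation of 40,000 trials used between-patient SD 1, within-patient SD 0.5, and stopping more likely in frailer patients and on the worse tolerated drink. The bias was 0.074 SD against the better tolerated drink when stopping precedes the scan. It was 0.063 SD against the worse tolerated drink when the session with complaints is scanned and any later session is missed. These averages are smaller because many simulated trials lose nobody. The complete-pair bias was below 0.001 SD in both.

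**Smallest attainable two-sided p-values**

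| Test | Formula | Result |
|---|---|---|
| Mann-Whitney, 6 v 5 | 2 / C(11,6) = 2/462 | 0.0043 |
| Signed-rank, 6 pairs | 2 / 2⁶ | 0.031 |
| Signed-rank, 5 pairs | 2 / 2⁵ | 0.0625 |

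**The case against.** The strongest reply is that 8.5 only says data are retained, which is sound practice, and that the harm comes from the unpaired test in 10.2. This is largely right about cause. Under a paired test the lone session would fall out of the contrast, so 8.5 alone does not bias it. But the protocol fixes both sentences. Correcting the test alone would still leave the lone session free to enter the medians and ranges.

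A second reply is that handling of incomplete pairs belongs in an analysis plan that is not shown. Mere silence would indeed be no finding. Here, however, the protocol states an inclusion rule and a test, and following both as written produces the problem.

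A reader might infer that the rule always works against the better tolerated drink, and so against a drink that prevents complaints. The documents do not support that. Session III is the last session, so stopping a bout there need not be a withdrawal, and the protocol does not say that bout 2 is then cancelled. A patient who leaves after a scanned session II biases the contrast the other way.

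It is also an assumption that the patient who leaves has the poorest spectroscopy values. The introduction reports larger Pi and PCr changes in patients than in controls, but no impairment of mitochondrial ATP synthesis, and nothing that relates severity among patients to these measures. The premise is weakest for the recovery rate constants.

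**Conclusion.** The point holds in a limited form and is a cheap improvement. Sections 8.5, 10.1 and 10.2 together allow a one-session patient to count on one drink's side, which undoes the within-patient comparison for that patient. The direction depends on when the patient leaves. The size is about 0.2 SD if the most affected of six is lost. That figure is conditional on such a loss and on assumed correlations of 0.5 to 0.9; averaged over assumed stopping patterns it is nearer 0.07 SD, of either sign. The signs and the exact p-value limits are firm; the SD figures are illustrative.

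A reader might also conclude that complete pairs are free of bias. They are so only when stopping reflects the patient's general severity. If it depends on that session's own value, some bias remains, though less than in the unpaired comparison.

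**What to change.** State in section 8.5 or 10 that:

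- the drink contrast is within-patient, and both it and the by-drink medians and ranges use patients with data under both drinks;
- data from a patient with one session are listed individually and not pooled;
- a sensitivity analysis gives the uncompleted session the worst rank, so that the patient stays in the comparison. Say in advance whether a session never attended counts as uncompleted, because there the worst rank would fall on the drink that did not provoke the complaints.

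A within-patient model that keeps all data is an acceptable alternative and fits the intent of 8.5. Stopping is already captured by drink through the completion endpoints in 8.1.2.

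The change takes a few sentences and no new data. Its cost is that the main contrast loses the incomplete pair. With five pairs a two-sided signed-rank test cannot go below p = 0.0625, so the 0.05 level in 10.2 would be out of reach for that test; the protocol should say so.

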8.6 Follow-up of subjects withdrawn from treatment

Patients who decide to withdraw from the study will be followed at the outpatient clinic at regular intervals. The follow-up scheme will remain similar to the scheme that was followed before participation in the study. Withdrawal from the study has no consequences for treatment and follow-up of the patients.

8.7 Premature termination of the study

Patients will have to terminate the study prematurely in the unlikely event of (symptoms of) hypoglycaemia during exercise. Dextrose tablets will be available to increase the blood glucose concentration in case of such a hypoglycaemia.

9. SAFETY REPORTING

9.1 Section 10 WMO event

In accordance to section 10, subsection 1, of the WMO, the investigator will inform the subjects and the reviewing accredited METC if anything occurs, on the basis of which it appears that the disadvantages of participation may be significantly greater than was foreseen in the research proposal. The study will be suspended pending further review by the accredited METC, except insofar as suspension would jeopardise the subjects' health. The investigator will take care that all subjects are kept informed.

9.2 Adverse and serious adverse events

Adverse events are defined as any undesirable experience occurring to a subject during the study, whether or not considered related to prolonged moderate-intensity exercise or MRS-analysis. All adverse events reported spontaneously by the subject or observed by the investigator or his staff will be recorded.

A serious adverse event is any untoward medical occurrence or effect that at any dose:

- results in death;
- is life threatening (at the time of the event);
- requires hospitalisation or prolongation of existing inpatients' hospitalisation;
- results in persistent or significant disability or incapacity;
- is a congenital anomaly or birth defect;
- is a new event of the trial likely to affect the safety of the subjects, such as an unexpected outcome of an adverse reaction, lack of efficacy of an IMP used for the treatment of a life threatening disease, major safety finding from a newly completed animal study, etc.

All SAEs will be reported through the web portal *ToetsingOnline* to the accredited METC that approved the protocol, within 15 days after the sponsor has first knowledge of the serious adverse reactions.

SAEs that result in death or are life threatening should be reported expedited. The expedited reporting will occur not later than 7 days after the responsible investigator has first knowledge of the adverse reaction. This is for a preliminary report with another 8 days for completion of the report.

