late evening snack or meal of their choice in correspondence with their individual record of maximal fasting duration, given a start time of the study at 08:00 am the following day. Patients will be allowed the same light breakfast according their normal diet before they will receive the caloric drive before the test. The breakfast will be the same for session II and III.

No adverse effects of this study are expected. Of the listed interventions that are proposed here, all but one – i.e., ingestion of the ketone caloric drink - have previously been included and approved in clinical investigations of metabolic myopathy patients by members of the investigative team in Amsterdam, Utrecht and/or Groningen: venipuncture and microbiopsy of the quadriceps muscle prior to and after exercise (protocol 04/1984 (MCADD; AMC Amsterdam); protocol **NL41313.042.12 (MCADD; UMCG)**); bouts of prolonged bicycle exercise outside and inside a MR scanner including in vivo MR spectroscopic data collection (protocol **12-211/K (VLCADD; UMC Utrecht; protocol NL41313.042.12 (MCADD; UMCG)**).

Of the interventions, only the **burden** of collecting tissue samples from the quadriceps muscle by microbiopsy is rated as moderate (as opposed to ratings of nil to minor burden for all other interventions¹). As such, this intervention will only be performed on a voluntary basis; it will not affect enrollment in the study. Muscle tissue sampling is, however, needed – and therefore desirable - to test the secondary hypothesis that NK boosts muscular mitochondrial function specifically at the level of substrate supply to the TCA cycle. Without the biopsy data, this secondary hypothesis cannot be validated. It would be highly desirable to know the outcome of that test since the information is needed to develop a proper mechanistic understanding of any therapeutic value of ketone administration in human metabolic myopathies such as fatty acid oxidation defects. On these grounds, the burden of microbiopsy is considered justifiable.

The **safety** of the nutritional drinks that will be administered and the expected acute, transient mild ketosis (concentrations of ketone bodies < 3 mM) has been thoroughly tested and documented in healthy subjects (see references 9,10). The drink has been designated as 'GRAS' (= Generally Recognized as Safe) by the Federal Drug Administration of the

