8.1.2 Secondary study parameters/endpoints

- completion of 40 min upright bicycling bout at FATMAX (yes/no; if no, #minutes)
- completion of 5 min supine bicycling bout at FATMAX in scanner (yes/no; if no, #minutes)
- subjective fatigue and muscle ache score after each exercise bout (scale 0-10) and 24 hours after exercise
- blood levels of 3-OH butyrate, acetoacetate, acylcarnitines, glucose, lactate and pH prior to and post-exercise.
- optional: muscle levels of glycogen, lactate, 3-OH butyrate, and (very) long (C18-C14) to medium (C12-C8) to short chain (C6-C2) acetyl-carnitines prior to and immediately post-exercise (on a patient-voluntary basis)

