9.2.1 Suspected unexpected serious adverse reactions (SUSAR)

Chapter-9.2.2 is not applicable for this study.

Adverse reactions are all untoward and unintended responses to an investigational product related to any dose administered.

Unexpected adverse reactions are adverse reactions, of which the nature, or severity, is not consistent with the applicable product information (e.g. Investigator's Brochure for an unapproved IMP or Summary of Product Characteristics (SPC) for an authorised medicinal product).

The sponsor will report expedited the following SUSARs through the web portal *ToetsingOnline* to the METC:

- SUSARs that have arisen in the clinical trial that was assessed by the METC;
- SUSARs that have arisen in other clinical trials of the same sponsor and with the same medicinal product, and that could have consequences for the safety of the subjects involved in the clinical trial that was assessed by the METC.

The remaining SUSARs are recorded in an overview list (line-listing) that will be submitted once every half year to the METC. This line-listing provides an overview of all SUSARs from the study medicine, accompanied by a brief report highlighting the main points of concern.

The expedited reporting of SUSARs through the web portal *ToetsingOnline* is sufficient as notification to the competent authority.

The sponsor will report expedited all SUSARs to the competent authorities in other Member States, according to the requirements of the Member States.

The expedited reporting will occur not later than 15 days after the sponsor has first knowledge of the adverse reactions. For fatal or life threatening cases the term will be maximal 7 days for a preliminary report with another 8 days for completion of the report.

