11.4 Benefits and risks assessment, group relatedness

In clinical practice, many patients with VLCADD wonder to which extent they are able to exercise safely. Any means of boosting this capacity will greatly improve the quality of life and long-term health in this patient population. Acute nutritional ketosis after ingestion of a novel edible ketone ester is a very promising novel therapy towards this aim and has already been tested with positive effects in human athletes. This study will gain insight whether a sound metabolic basis exists for its therapeutic use in this patient population.

No adverse effects of this study are expected. Of the listed interventions that are proposed here, all but one – i.e., ingestion of the ketone caloric drink - have previously been included and approved in clinical investigations of metabolic myopathy patients by members of the investigativce team in Amsterdam, Utrecht and/or Groningen: venipuncture and microbiopsy of the quadriceps muscle prior to and after exercise (protocol **04/1984 (MCADD; AMC Amsterdam)**); protocol **NL41313.042.12 (MCADD; UMCG)**); bouts of prolonged bicycle exercise outside and inside a MR scanner including in vivo MR spectroscopic data collection (protocol **12-211/K (VLCADD; UMC Utrecht; protocol NL41313.042.12 (MCADD; UMCG))**). Of the interventions, only the **burden** of collecting tissue samples from the quadriceps muscle by microbiopsy is rated as moderate (as opposed to ratings of nil to minor burden for

all other interventions²). As such, this intervention will only be performed on a voluntary basis; it will not affect enrollment in the study. Muscle tissue sampling is needed to test the secondary hypothesis that NK boosts muscular mitochondrial function specifically at the level of substrate supply to the TCA cycle; therefore, the burden of micro biopsy is considered justifiable.

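### Section 9.2 captures drink-related events only if volunteered or observed, and its relatedness clause omits the study drinks, so mild intolerance after discharge would probably be under-reported

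*Protocol*

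**What the plan says.** Section 9.2 opens with a wide definition: "Adverse events are defined as any undesirable experience occurring to a subject during the study". It continues "whether or not considered related to prolonged moderate-intensity exercise or MRS-analysis". The collection rule follows: "All adverse events reported spontaneously by the subject or observed by the investigator or his staff will be recorded".

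Section 11.4 (and the Summary, in the same terms) says of the listed interventions that "all but one – i.e., ingestion of the ketone caloric drink - have previously been included and approved in clinical investigations". Section 1 presents the trial as the first clinical investigation of the ketone drink in VLCADD, and section 11.4 rests the drink's safety on data in healthy subjects. Section 5.1 lists the drink and placebo as the investigational treatment.

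After each of sessions II and III a co-investigator "will call each subject to evaluate subjective fatigue and muscle complaints after the subject left the test facility" (section 3). The matching patient-reported endpoint in section 8.1.2 is "subjective fatigue and muscle ache score after each exercise bout (scale 0-10) and 24 hours after exercise".

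Section 9.2.1, on suspected unexpected serious adverse reactions, begins "Chapter-9.2.2 is not applicable for this study". It then defines adverse reactions as responses to an investigational product and sets reporting times. Section 9.3 asks for a yearly list of suspected serious adverse reactions and a safety analysis.

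**The concern.** The clause that lists possible causes names two procedures the team has already used and leaves out the intervention under test. Collection is passive, and the one planned contact after the patient goes home has a stated content that does not touch the drink. A patient with nausea or stomach complaints that evening could be telephoned the next day, answer everything asked, and leave no record.

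The trial describes itself as a first step toward therapeutic use in this disorder. How well VLCADD patients tolerate the drink is information it could produce at almost no cost. With six patients, one unrecorded complaint would change the description of tolerability.

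**Working it through.** The point is about wording, and the protocol gives no figure to reproduce. The check is to follow a drink-related event through the text.

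**1. Is it an adverse event?** Yes. The definition covers every undesirable experience during the study, and the whether-or-not construction sets no causal limit. The omission in the clause does not remove drink events from the definition.

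**2. Would it be recorded?** That depends on where it happens.

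| Period | Route to a record | Drink tolerance asked about? |
|---|---|---|
| On site: about 5 hours, including 3 hours of rest after exercise (section 3) | Volunteered or observed (9.2) | No; fatigue and muscle-ache scores only (8.1.2) |
| From discharge to the 24-hour call | Volunteered only; staff are not present | No |
| During the call | Volunteered | No; fatigue and muscle complaints only (section 3) |

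The unobserved period is about 24 hours if the call is timed from the end of the session. It is about 24 − 3 = 21 hours if timed from the end of exercise; the protocol does not say which. In that period the record depends wholly on the patient raising the matter unprompted. This gap comes from the collection rule and the content of the call, not from the definition.

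**3. Would it be attributed to the drink?**
- By period: yes, for a dated event. Each session uses one drink, sessions II and III are 7 days apart (section 3), and the order is recorded (section 8.2).
- By causality judgement, serious events: partly provided for. Section 9.2.1 defines reactions to an investigational product, and section 9.3 requires serious ones to be listed. But 9.2.1 opens by declaring a section 9.2.2 inapplicable, and the protocol contains no 9.2.2, so it is unclear whether the 9.2.1 text is meant to apply. Sections 6 and 7, on investigational medicinal and non-investigational products, are both marked not applicable, which does not help the reader settle the drink's status.
- By causality judgement, non-serious events: nothing is set out. The only relatedness wording is the clause in 9.2, which does not mention the drink.

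**4. How much is affected?** 6 patients × 2 sessions = 12 administrations, each followed by two existing contacts (end of the 3-hour rest, 24-hour call). That makes 12 × 2 = 24 opportunities to ask about the drink, and the protocol specifies the question at none of them.

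**The case against.** The strongest reply is that little is broken. The definition already captures drink events. Collection by spontaneous report and observation is a recognised method. Tolerability is not among the objectives in section 2. The protocol gives a reason for limited attention to it: use in over 200 people without adverse effects, a published tolerability profile and food status in the USA (section 1). Fixed question sets are often left to the case report form. The 9.2.2 line sits in a section on serious reactions and has no bearing on mild nausea at home.

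Most of this is fair and limits the point. Two things remain. The prior evidence cited for safety is in healthy subjects, while this is a first use in VLCADD patients from age 16. And the protocol is not silent on collection: it states a passive method and a call whose content leaves the drink out.

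Three stronger readings are tempting, and the documents do not support them:
- *Drink events fall outside the definition.* They do not; the definition has no causal limit.
- *Events cannot be assigned to ketone or placebo.* They can, from the event date and the recorded drink order.
- *A vomited drink would remove ketosis unnoticed.* The drink is taken on site under supervision. Blood 3-OH butyrate before and after exercise is a listed endpoint (8.1.2), with up to 7 samples per session (8.3), so failed ketosis should be visible. Those samples would not show its cause, nor a partly lost placebo drink, but the main comparison is not exposed to a hidden loss of ketosis.

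**Conclusion.** The point holds in a limited form. The relatedness clause in 9.2 omits the study drinks, the ketone drink being the one intervention new to these patients. Capture is passive, the 24-hour call is confined to fatigue and muscle complaints, and causality against the drink is not provided for when an event is non-serious. The likely consequence is under-reporting of mild drink intolerance after discharge, over 12 administrations. The protocol gives no basis for estimating how many events would be missed.

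No endpoint, analysis or comparison between drinks is invalidated. This is a cheap improvement to what the trial collects, plus one reference to correct. It rests on two assumptions: that no case report form already adds solicited tolerance questions, and that patients volunteer mild symptoms less often than they report them when asked.

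**What to change.** 1. In 9.2, extend the relatedness clause to name both study drinks and the biopsy alongside exercise and MRS. Record relatedness to the drink for every event, by session, including non-serious ones.
2. Ask one fixed set of drink-tolerance questions, including whether vomiting occurred and when, at the end of the 3-hour rest and in the existing 24-hour call. Word it identically for both sessions. This matters because, under section 8.2, the person who randomises and records the drink order also helps conduct the sessions, and free-form questioning could differ between drinks.
3. Tabulate the answers by drink, using the recorded order.
4. Reconcile the line about 9.2.2 with the text of 9.2.1 and with 9.3, so that it is clear which reporting provisions apply.

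The cost is protocol wording and about two minutes per contact: 2 minutes × 24 contacts = 48 minutes over the whole trial. No visit, sample or procedure is added.
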